14.8 MISSING DATE INFORMATION FOR PRIOR OR CONCOMITANT MEDICATIONS

For prior or concomitant medications, including rescue medications, incomplete (ie, partly missing) start dates and/or stop dates will be imputed. When the start date and the stop date are both incomplete for a patient, the start date will be imputed first.

14.8.1 Incomplete Start Date

The following rules will be applied to impute the missing numeric fields for an incomplete prior or concomitant medication start date. If the stop date is complete (or imputed) and the imputed start date is after the stop date, the start date will be imputed using the stop date.

Missing month and day

- If the year of the incomplete start date is the same as the year of the first dose of study treatment, the month and day of the first dose of study treatment will be assigned to the missing fields
- If the year of the incomplete start date is before the year of the first dose of study treatment, *December 31* will be assigned to the missing fields
- If the year of the incomplete start date is after the year of the first dose of study treatment, *January 1* will be assigned to the missing fields

Missing month only

- If only the month is missing, the day will be treated as missing and both the month and the day will be replaced according to the above procedure

Missing day only

- If the month and year of the incomplete start date are the same as the month and year of the first dose of study treatment, the day of the first dose of study treatment will be assigned to the missing day
- If either the year of the incomplete start date is before the year of the date of the first dose of study treatment or if both years are the same, but the month of the incomplete start date is before the month of the date of the first dose of study treatment, the last day of the month will be assigned to the missing day.
- If either the year of the incomplete start date is after the year of the date of the first dose of study treatment or if both years are the same, but the month of the incomplete start date is after the month of the date of the first dose of study treatment, the first day of the month will be assigned to the missing day

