5.3 Inclusion Criteria

Participants should:

[figure not shown]
1. Be twenty-two (22) years of age or older at the Screening Visit

2. At the Screening and Baseline Visits, have a Standard Patient Evaluation for Dryness (SPEED) [REDACTED]
3. In at least one eye, meet all of the following objective measures in the same eye:
 - A basal Schirmer test [REDACTED]
 - [REDACTED]
 - [REDACTED]
 - Tear film breakup time (TBUT) \geq [REDACTED]
4. Have used an artificial tear product, lid hygiene [REDACTED]; omega-3 supplementation; antibiotics [REDACTED] for the treatment of dry eye disease or meibomian gland disease within one year of the Screening Visit
 - [REDACTED]
 - [REDACTED]
 - [REDACTED]

[figure not shown]

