7.0 DEMOGRAPHICS AND OTHER BASELINE CHARACTERISTICS

Demographic parameters (age; age group (<65 vs ≥ 65, race; ethnicity; sex), baseline characteristics (wearing contact lenses before seven days prior to the study) and other disease characteristics (Sjogren's syndrome) will be summarized descriptively by treatment group and overall for the ITT populations. Continuous variables will be summarized by number of patients and mean, SD, Q1/Q3, median, minimum, and maximum values. Categorical variables will be summarized by number and percentage of patients. A subject listing of demographics and baseline characteristics will be provided.

Medical and surgical histories will be coded using the *Medical Dictionary for Regulatory Activities*, version 20.1 or newer. The number and percentage of patients with Ocular and Non-Ocular medical and surgical histories at baseline in each system organ class and preferred term will be summarized by treatment group for the Safety Population, separately. A subject listing for Surgical and Medical Histories will be provided.

Prior medication is defined as any medication taken before the date of the first dose of study treatment. *Concomitant medication* is defined as any medication taken on or after the date of the first dose of study treatment.

Both prior and concomitant medications will be coded using The Anatomical-Therapeutic-Chemical classification text from World Health Organization (WHO) Drug Dictionary. The use of prior and concomitant medications will be summarized by the number and percentage of patients in each treatment group for the Safety Population. If a patient took a specific medication multiple times or took multiple medications within a specific therapeutic class, that patient would be counted only once for the coded drug name or therapeutic class. Formulations (including salts, esters, etc) containing the same active ingredient will be pooled under the coded drug name of the base compound. Medications containing multiple active ingredients of different coded drug names will be reviewed during the study and may be pooled under a single coded drug name for analyses. A subject listing for prior and concomitant medications will be provided.

The Anatomical-Therapeutic-Chemical classification text from World Health Organization (WHO) Drug Dictionary, MAR17 or newer, will be used to classify prior and concomitant medications by therapeutic class and drug name.

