14.8.2 Incomplete Stop Date

The following rules will be applied to impute the missing numeric fields for an incomplete prior or concomitant medication stop date. If the date of the last dose of study treatment is missing, impute it as described in Section 14.4. If the imputed stop date is before the start date (imputed or nonimputed start date), the imputed stop date will be equal to the start date.

Missing month and day

- If the year of the incomplete stop date is the same as the year of the last dose of study treatment, the month and day of the last dose of study treatment will be assigned to the missing fields
- If the year of the incomplete stop date is before the year of the last dose of study treatment, *December 31* will be assigned to the missing fields
- If the year of the incomplete stop date is after the year of the last dose of study treatment, *January 1* will be assigned to the missing fields

Missing month only

- If only the month is missing, the day will be treated as missing and both the month and the day will be replaced according to the above procedure

Missing day only

- If the month and year of the incomplete stop date are the same as the month and year of the last dose of study treatment, the day of the last dose of study treatment will be assigned to the missing day
- If either the year of the incomplete stop date is before the year of the date of the last dose of study treatment or if both years are the same, but the month of the incomplete stop date is before the month of the date of the last dose of study treatment, the last day of the month will be assigned to the missing day
- If either the year of the incomplete stop date is after the year of the date of the last dose of study treatment or if both years are the same, but the month of the incomplete stop date is after the month of the date of the last dose of study treatment, the first day of the month will be assigned to the missing day

15.0

CHANGES TO ANALYSES SPECIFIED IN PROTOCOL

None

Allergan PLC
TrueTear™

16.0 **REFERENCES**

None

17.0 **AMENDMENTS**

Date	Revision Number	Primary Author	Description of Change
07 March 2018	1	[REDACTED]	Initial Approval
25 Sept 2018	2	[REDACTED]	
• [REDACTED]• [REDACTED] 
• Administrative changes

ALLERGAN

1919-610-019 Analysis Plan

Date (DD/MMM/YYYY)/Time (PT)

[REDACTED]
[REDACTED]
[REDACTED]
[REDACTED]

Signed by:

[REDACTED]
[REDACTED]
[REDACTED]
[REDACTED]

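### SAP 14.8.1 dates a year-only, same-year start to first dose, so a product used to meet inclusion criterion 4 can lose its prior-medication status and, with a year-only stop, appear as on-study use

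*SAP*

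**What the plan says.** Protocol 5.3, criterion 4, admits people who have used an artificial tear, lid hygiene, omega-3 or antibiotic product "for the treatment of dry eye disease or meibomian gland disease within one year of the Screening Visit". Randomization and the first application follow at a later visit, Visit 2 (Day 0), under Protocol 8.1.5, 8.3 and 8.4.

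SAP 7.0 splits medications at first dose: "Prior medication is defined as any medication taken before the date of the first dose of study treatment", while concomitant medication "is defined as any medication taken on or after the date of the first dose of study treatment". The display is descriptive: "The use of prior and concomitant medications will be summarized by the number and percentage of patients in each treatment group", in the Safety Population.

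For partly missing dates, SAP 14.8 fixes the order: "When the start date and the stop date are both incomplete for a patient, the start date will be imputed first". For a start with month and day missing, SAP 14.8.1 applies this branch: "If the year of the incomplete start date is the same as the year of the first dose of study treatment", then "the month and day of the first dose of study treatment will be assigned to the missing fields". If the year is earlier, the start becomes December 31 of that year. If the imputed start falls after the stop, it is pulled back to the stop. For a year-only stop in the year of last dose, SAP 14.8.2 says "the month and day of the last dose of study treatment will be assigned to the missing fields". An imputed stop that would fall before the start is moved forward to the start.

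The visible text makes no exception for a product recorded at Screening.

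**The concern.** A product offered as evidence for criterion 4 must have been in use by Screening. The same-year branch of 14.8.1 nevertheless starts it on Day 0. Imputation normally fills in something unknown; here it contradicts something the record already establishes.

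Two separate errors can follow. An ongoing product is rightly shown as concomitant but drops out of the prior count. A product that stopped before Day 0 and has a year-only stop is shown as used through the treatment period, when it was not used then at all.

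At stake is the accuracy of the by-arm medication table. In an open-label comparison with a compress, a reader would naturally look there for other dry eye or MGD treatment in each arm.

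**Working it through.** The plan gives no figure to reproduce, so the check is a literal trace of the rules.

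**Inputs**
- Criterion 4: use precedes Screening, which precedes Day 0 (Protocol 5.3, 8.1.5).
- Classification: prior if taken before first dose, concomitant if taken on or after it (SAP 7.0).
- Imputation: start first, then stop (SAP 14.8, 14.8.1, 14.8.2).
- Assumed for illustration: Day 0 = 1 September 2017 and last dose 30 days later, 1 October 2017. Enrolment dates are not in the documents.
- Assumed Screening-to-Day 0 gap: 44 − 30 = 14 days, from the approximate participation and treatment lengths.

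**Trace**

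| Recorded start | Recorded stop | Imputed start | Stop used | Class |
|---|---|---|---|---|
| 2017 | 2017 | 1 Sep 2017 | 1 Oct 2017 | Concomitant only |
| 2017 | ongoing | 1 Sep 2017 | none | Concomitant only |
| 2017 | 12 Aug 2017 | 12 Aug 2017 | 12 Aug 2017 | Prior only |
| 2016 | 2016 | 31 Dec 2016 | 31 Dec 2016 | Prior only |
| 2016 | 2017 | 31 Dec 2016 | 1 Oct 2017 | Prior and concomitant |
| 2016 | ongoing | 31 Dec 2016 | none | Prior and concomitant |

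In the first two rows the start is known to be wrong. In the first row, a course that had ended before Day 0 also gains a false concomitant entry. The safeguard against a start after the stop is not triggered, because the stop has itself been placed at the last dose. The third row shows the safeguard working when the stop date is complete. In the fourth and sixth rows the class is consistent with what is recorded. In the fifth row prior status is kept, but the imputed stop would still be wrong if the product had ended before Day 0.

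Two edge cases:
- With Day 0 on 15 December 2017 the last dose is 14 January 2018. A year-only 2017 stop then becomes 31 December 2017, not the last dose, but the record is still concomitant only.
- For a 2017 start and a stop known only as July 2017, the text supports two results. Imputing the start first and then moving the stop forward under 14.8.2 gives 1 September for both, concomitant only. The 14.8.1 safeguard, which also refers to an imputed stop, gives 31 July for both, prior only.

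**Reach of the same-year branch**

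Share of the one-year qualifying window in Day 0's calendar year = (days from 1 January to the day before Screening) / 365, or zero if Screening falls in the previous year or on 1 January.

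- Day 0 on 15 June 2017: 151/365 = 41%
- 1 September 2017: 229/365 = 63%
- 31 December 2017: 350/365 = 96%
- 1 to 14 January 2018: 0%
- 1 February 2018: 17/365 = 5%

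This is the share of the window, not of records. Criterion 4 concerns use within the year, so a product may have been started earlier still.

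**Size per participant**

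Planned arm size = 70/2 = 35, so one misclassified participant is 1/35 = 2.9 percentage points. That holds only if the participant has no other entry under the same drug or class, since SAP 7.0 counts each patient once.

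**After the change**

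For a record with 2017 for both dates and Screening on 18 August 2017 (1 September − 14 days):
- Capping only the start gives 18 August to 1 October: prior is restored, but the concomitant flag remains.
- Capping the stop as well, when recorded as stopped, gives 18 August for both: prior only.

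Both caps are therefore needed.

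**The case against.** The strongest reply is that this is a conventional rule with narrow reach. SAP 14.7 uses the same first-dose assignment for adverse events, where leaning towards on-study is cautious. Only same-year, year-only starts without a complete stop before Day 0 are affected. Qualifying use precedes randomization, so date quality should not depend on arm and only chance imbalance is expected. No visible population or test uses the flag. All of this stands, and it keeps the point minor. The convention argument does not remove it: for adverse events the timing is unknown, while here use before Screening is known.

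It can also be said that SAP 7.0 speaks of when a medication was taken, not of its imputed start. Using imputed dates to classify is an inference, though no other use of them is visible.

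A reader might infer several stronger things that the documents do not support:
- **That all year-only qualifying therapies become on-study.** The December 31 branch and the safeguard for a complete stop rule this out.
- **That treatment washed out for the study is shown as taken.** Much of Protocol 5.3 and 8.5 is redacted, so no washout rule can be checked.
- **That criterion 4 would look unmet, or prohibited use would be declared.** Eligibility is decided before randomization (Protocol 8.1.5), entry deviations are coded and listed separately (SAP 7.0), and prohibited medication is handled as a withdrawal reason (Protocol 5.6).
- **That the treatment comparison is biased.** The exploratory effectiveness text is redacted, and nothing visible gives the medication table a formal role in it.

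**Conclusion.** The point holds in a limited form, as a minor correction. For a criterion 4 product with a start known only to the year of first dose and no complete stop before Day 0, the rule assigns a start known to be false, and known prior use is lost. The exception is a stop known to a month before Day 0, where the text allows either class. A false on-study entry needs more: the course must have ended before Day 0 and its stop must also be incomplete, typically year-only in the year of last dose.

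The visible consequence is confined to the descriptive by-arm table of prior and concomitant medications, at about 2.9 percentage points per affected participant. The number affected cannot be determined: it depends on how often dates are year-only and on when people enrolled, and the same-year branch covers anywhere from 0% to 96% of the qualifying window. The conclusion assumes that criterion 4 products are entered in the dated medication record and that imputed dates drive the classification. The documents show neither, and lid hygiene in particular may be recorded elsewhere.

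**What to change.** Add one sentence to each section:
- **SAP 14.8.1:** for any medication or therapy recorded at Screening, including products used to meet criterion 4, an imputed start may not be later than the Screening Visit date.
- **SAP 14.8.2:** if the product is recorded as stopped at Screening, an imputed stop may not be later than the Screening Visit date; if recorded as ongoing, it counts as both prior and concomitant.

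Apply the caps before comparing start with stop. Keep the first-dose and last-dose rules for medications first reported after Day 0. For those, it would help to state which tie-break applies when both dates are incomplete, since 14.8.1 and 14.8.2 pull in opposite directions.

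The cost is two sentences and a small programming change, with no new visits or participants. The downside is reliance on the CRF holding the visit of recording and the ongoing or stopped status. The documents do not show these fields, so confirm them first.

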14.8.2 Incomplete Stop Date

The following rules will be applied to impute the missing numeric fields for an incomplete prior or concomitant medication stop date. If the date of the last dose of study treatment is missing, impute it as described in Section 14.4. If the imputed stop date is before the start date (imputed or nonimputed start date), the imputed stop date will be equal to the start date.

Missing month and day

- If the year of the incomplete stop date is the same as the year of the last dose of study treatment, the month and day of the last dose of study treatment will be assigned to the missing fields
- If the year of the incomplete stop date is before the year of the last dose of study treatment, *December 31* will be assigned to the missing fields
- If the year of the incomplete stop date is after the year of the last dose of study treatment, *January 1* will be assigned to the missing fields

Missing month only

- If only the month is missing, the day will be treated as missing and both the month and the day will be replaced according to the above procedure

Missing day only

- If the month and year of the incomplete stop date are the same as the month and year of the last dose of study treatment, the day of the last dose of study treatment will be assigned to the missing day
- If either the year of the incomplete stop date is before the year of the date of the last dose of study treatment or if both years are the same, but the month of the incomplete stop date is before the month of the date of the last dose of study treatment, the last day of the month will be assigned to the missing day
- If either the year of the incomplete stop date is after the year of the date of the last dose of study treatment or if both years are the same, but the month of the incomplete stop date is after the month of the date of the last dose of study treatment, the first day of the month will be assigned to the missing day

15.0

CHANGES TO ANALYSES SPECIFIED IN PROTOCOL

None

Allergan PLC
TrueTear™

16.0 **REFERENCES**

None

17.0 **AMENDMENTS**

Date	Revision Number	Primary Author	Description of Change
07 March 2018	1	[REDACTED]	Initial Approval
25 Sept 2018	2	[REDACTED]	
• [REDACTED]• [REDACTED] 
• Administrative changes

ALLERGAN

1919-610-019 Analysis Plan

Date (DD/MMM/YYYY)/Time (PT)

[REDACTED]
[REDACTED]
[REDACTED]
[REDACTED]

Signed by:

[REDACTED]
[REDACTED]
[REDACTED]
[REDACTED]

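### When both medication dates are partial, SAP 14.8.1 and 14.8.2 move opposite dates, and the stated order can report a medication stopped before treatment as concomitant only

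*SAP*

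**What the plan says.** - **Order (SAP 14.8).** "When the start date and the stop date are both incomplete for a patient, the start date will be imputed first".
- **Start rule (SAP 14.8.1).** For a start with month and day missing, in the same year as first dose, "the month and day of the first dose of study treatment will be assigned to the missing fields". The tie-break reaches a stop that is "complete (or imputed) and the imputed start date is after the stop date, the start date will be imputed using the stop date".
- **Stop rule (SAP 14.8.2).** For a stop with only the day missing, in a month before the last-dose month, "the last day of the month will be assigned to the missing day". The tie-break here reads "If the imputed stop date is before the start date (imputed or nonimputed start date), the imputed stop date will be equal", so the stop moves forward and takes the start's date.
- **Classification (SAP 7.0).** A prior medication is one taken before the first-dose date. A concomitant medication "is defined as any medication taken on or after the date of the first dose of study treatment". Both are tabulated as number and percentage of patients by arm in the Safety Population, and a subject listing is planned.

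Both 14.8.1 and 14.8.2 treat a date with the month missing as if the day were missing too, so such dates count below as year-only.

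**The concern.** If one date is complete, only one tie-break can operate. If both are partial and the imputed start is later than the imputed stop, the two sentences describe the same pair and move different ends of it. In the stated order, no imputed stop exists yet when the start is handled. The words *(or imputed)* in 14.8.1 therefore never act, and 14.8.2 settles the pair by moving the stop forward.

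That can discard the better-recorded date. A year-only start says little, whereas a stop with month and year is real information. Replacing that month with the first-dose date reports a therapy known to have ended before treatment as used on Day 0.

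The pattern is plausible here. Protocol 5.3, criterion 4, requires treatment for dry eye or meibomian gland disease within one year of Screening, so most participants should have recent eye-directed therapy to report, some perhaps from memory. The by-arm medication tables tell the reader of an open-label comparison what else was in use during treatment.

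**Working it through.** The documents give no figure to reproduce. The check applies the rules to dates.

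**Inputs.** The imputation rules and tie-breaks are from SAP 14.8 to 14.8.2, and the class definitions from SAP 7.0. Dosing dates are assumptions, with last dose about 30 days after first dose as in SAP 3.0.

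**Worked record.** Assume first dose 15 Aug 2017 and last dose 14 Sep 2017. Start is recorded as 2017, stop as Mar 2017.

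1. Start: same year as first dose, so imputed as 15 Aug 2017.
2. Stop: March precedes the last-dose month, so imputed as 31 Mar 2017.
3. 31 Mar is before 15 Aug, so the dates cross.
4. Tie-break 14.8.1 would give 31 Mar to 31 Mar, which is prior only.
5. Tie-break 14.8.2, reached by the stated order, gives 15 Aug to 15 Aug, which is concomitant only. The recorded March is lost.

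**All partial-date pairs.** Each date was taken as year-only or month-and-year, over the year before, of and after first dose. Pairs in which the start could not precede the stop were dropped, leaving 816 patterns for each dosing scenario. A conflict is an imputed stop before the imputed start.

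| Assumed first / last dose | Conflicts | Year-only start, stop month recorded | Year-only stop, start month recorded | Class differs between tie-breaks |
|---|---|---|---|---|
| 15 Sep 2017 / 15 Oct 2017 | 32 | 19 | 13 | 8 |
| 15 Dec 2017 / 14 Jan 2018 | 33 | 22 | 11 | 11 |
| 10 Jan 2018 / 9 Feb 2018 | 32 | 11 | 21 | 0 |

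The September row follows by hand:

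- Start 2016 is imputed as 31 Dec 2016 and conflicts with stops Jan to Nov 2016: 11.
- Start 2017 is imputed as 15 Sep and conflicts with stops Jan to Aug 2017: 8.
- Stop 2017 is imputed as 15 Oct and conflicts with starts Nov and Dec 2017: 2.
- Stop 2018 is imputed as 1 Jan 2018 and conflicts with starts Feb to Dec 2018: 11.
- Total: 11 + 8 + 2 + 11 = 32.

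**Which conflicts change class.** Only a year-only start in the first-dose year with a stop month before the first-dose month. The number of such stop months is the first-dose month minus 1: 8 for September, 11 for December, 0 for January, and by the same rule 1 for February. All other conflicts shift dates within one class. For example, start 2016 with stop Mar 2016 becomes 31 Mar or 31 Dec 2016, and is prior either way.

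**Which date is less complete.** The two middle columns add up to the conflicts in each row (19 + 13 = 32, 22 + 11 = 33, 11 + 21 = 32). In every conflict listed, exactly one date is year-only and the other has a recorded month.

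**The case against.** **The order gives one answer.** A reader might infer that two programmers following the SAP must produce different tables. The documents do not support that. Section 14.8 fixes the sequence, and in sequence 14.8.2 decides. What remains is a phrase in 14.8.1 with no effect, which could mislead a programmer who tries to honour it, and a wrong result from the order itself.

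**Most conflicts do not reach the tables.** This stands. SAP 7.0 reports counts of patients, so a date shift within a class changes nothing there. Even a class change alters a count only if no other record already places that patient in the same row, because a patient is counted once per coded drug name or therapeutic class.

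**Using 14.8.1 throughout looks like the simple repair, but is not.** With first dose 15 Sep 2017 and last dose 15 Oct 2017, start Nov 2017 and stop 2017 are imputed as 1 Nov and 15 Oct. The 14.8.1 tie-break would pull the start back to 15 Oct and lose the recorded November. It overwrites a recorded start month in 13 of 32 conflicts for that dosing, and in 21 of 32 for first dose 10 Jan 2018. Many of these starts fall after the roughly 44 days of participation, so they should be rare, but the rule is not clean.

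**No effect on an effectiveness result can be claimed.** A reader might infer a biased comparison between devices. No visible analysis uses these dates, and SAP Section 9 is partly redacted, so nothing can be said about it either way.

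**Conclusion.** The point holds as a minor data-handling error. The tie-breaks in 14.8.1 and 14.8.2 are opposed, and the stated order lets 14.8.2 decide. For a year-only start in the first-dose year and a recorded stop month before the first-dose month, that order replaces a known pre-treatment stop month with the first-dose date and turns a prior medication into a concomitant-only one.

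The visible effect is confined to the descriptive medication summaries by arm and depends on the calendar: 8 of 32 conflict patterns for a mid-September first dose, 11 of 33 for mid-December, none for January, and a single stop month for February. These are counts of date patterns under assumed dosing dates, not patient frequencies. The documents do not say how many records have both dates partial; among about 70 participants it could be none.

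**What to change.** Three edits to the SAP:

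1. In 14.8, state that when both dates are partial, both are imputed first. If the imputed start is then after the imputed stop, the less complete date is set equal to the more complete one: a year-only start takes the imputed stop, and a year-only stop takes the imputed start.
2. In 14.8.1, limit the tie-break to a complete stop date, as SAP 14.7 already does for partly missing adverse event start dates.
3. In 14.8.2, limit the tie-break to a complete start date.

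This resolves every conflict in the table above without overwriting a recorded month. In the worked record, the start takes the imputed stop, giving 31 Mar to 31 Mar 2017, prior only. For start Nov 2017 and stop 2017, the stop takes the imputed start and November is kept.

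The cost is a few sentences and one program check, with no change to data collection. Reporting how many records had both dates partial and crossed after imputation would show whether the correction mattered.
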